### 6.3.2. Recruitment and enrolment

Recruitment of potential subjects will begin once approval has been obtained from the Ethics Committee and the Danish Medicine Agency

Recruitment will take place using subject records from the site as well as via www.forsøgsperson.dk and, if necessary, through advertisements in local newspapers and educational institutions.

Before the investigation starts, investigator and all study nurses will receive verbal information about the investigation, as well as instruction on investigation procedures and completion of the CRF. Before the investigation can begin at a site, the investigator must sign the current Clinical Investigation Plan to declare that he will conduct the investigation according the plan.

### Subjects recruited via subject records

Investigator identifies potential subjects in relation to in- and exclusion criteria through subject records kept at the site (from previous clinical studies involving healthy subjects). The identified potential subjects will receive by mail or e-mail the Subject Invitation Letter attached the written subject information and "Forsøgspersoners rettigheder i et sundhedsvidenskabeligt forskningsprojekt". If the subject is interested in participating, he is encouraged to contact the site and visit 0 is arranged (informed consent process, see section 13).

## Subjects recruited via www.forsøgsperson.dk, local newspapers or educational institutions

Subjects may furthermore be recruited through www.forsøgsperson.dk where potential subjects can gather information on clinical studies. If necessary, they may also be recruited through local newspapers and educational institutions. Interested potential subjects will contact the Clinical Manager or a representative hereof. In- and exclusion criteria are preliminary reviewed and general questions regarding the study are answered. If the potential subject is interested in participating, he will receive the written subject information and "Forsøgspersoners rettigheder i et sundhedsvidenskabeligt forskningsprojekt" and contact information is passed on to the investigator or study nurse, who will then contact the potential subject. If he still wishes to participate, visit 0 is arranged.

Potential subjects recruited in one of the above ways will, at visit 0, go through the informed consent process (see section 13). Once enrolled in the study, the subject may then continue to formal in- and/or exclusion.

#### 6.3.3. Subject withdrawal criteria

The subject can withdraw from the investigation at any time for whatever reason without any consequences for their future treatment outside the clinical investigation. The investigator may withdraw a subject from the investigation at any time if he assesses withdrawal to be in the subject's best interest.

The investigator must withdraw a subject from the investigation for the following reasons:

- If a subject's safety and well-being is compromised by further participation
- Non-compliance with the CIP impacting the scientific integrity of the investigation

Withdrawn subjects will not be replaced by new subjects.

A subject who is withdrawn from the investigation, for any reason, will be encouraged to contact the investigator if problems arise that he believes are related to the investigation. A subject who has not experienced adverse events will not be followed up. For subjects who experience adverse events, see section 14.

At termination, due to above reasons investigator or study nurse completes the termination form and sponsor is informed.

#### 6.3.4. Point of enrolment

A subject is considered enrolled in the investigation when he has signed and dated the Informed Consent Form.

The expected duration of involvement for each subject is described in section 6.1.

## 6.3.5. Total expected duration of the clinical investigation

The dates in table 7 below are approximate. No subjects will be enrolled before the required approval has been obtained from the Ethics Committee of the Capital Region of Denmark and Lægemiddelstyrelsen. The same committees will be informed of investigation termination within 90 days hereof (unless the investigation is terminated prematurely where information is then given 15 days after termination, including the reason for the premature termination).

Activity	Estimated time	
First subject enrolled	August 2019	-
Last subject enrolled	February 2020	
Last subject completed	March 2020	
Final Report	March 2021	

Table 7: Estimated timeline

### 6.3.6. Total number of subjects

During the investigation period, there will be enrolled 22 subjects based on a drop-out rate of 20%. A subject is considered enrolled in the investigation when he has signed and dated the Informed Consent Form.

#### 6.4. Procedures

## 6.4.1. Clinical investigation-related procedures

Before initiation of the clinical investigation, the sponsor is provided with key personnel's current signed and dated CVs to verify their qualifications. Key site personnel are those who treat or evaluate subject data in the clinical investigation. The sponsor will ensure that all site personnel are trained in using the investigational device as well as in the investigation procedures, how to complete the CRFs, the procedure for reporting an adverse event or serious adverse event (how, when, to whom), and who to contact in the case of an emergency related to the investigational device.

#### Study period

During the study period, each subject has three visits: visits 0, 1 and 2. Visit 0 (inclusion) and visit 1 can be the same day, as follows:

### Visit 0 (Inclusion):

Subject will be given information about the investigation and will sign the Informed Consent Form and the Letter of Authority (see section 13). It is ensured that in- and exclusion criteria are met, including urine analysis (leukocytes, nitrite and erythrocytes) with multistix (Multistix 7, Siemens).

Enrolled subjects are allocated a subject number, and will hereafter be randomised per the study design and demographics, baseline data and concomitant medication is recorded.

## Visit 1 (0-7 days after visit 0):

Subject is asked about symptoms for urinary tract infections and use of analgesics up to 24 hours prior to the visit. An urine sample is collected, and microscopic haematuria is measured before catheterisation is initiated. If the subject presents negative for urinary tract infections, use of analgesics and microscopic haematuria, the subject will be catheterised with product 1 per randomisation. The subject is offered something to drink and then asked for a urine sample to measure if any microscopic haematuria is present. The nurse registers relevant answers in the eCRF, including possible adverse events. In addition, subject registers the endpoints regarding discomfort (VAS-scale) during catheterisation and again after first urination and the nurse measure and enters the subject's assessments in the eCRF. Next visit is scheduled.

#### Visit 2 (4-15 days after last visit):

The procedure for visit 1 is repeated in visit 2.

After completed procedure, the termination form will be completed by investigator or study nurse. If the subject develops symptoms of urinary tract infection or has visual blood in the urine during the investigation he will be treated per standard hospital procedure.

It is not considered necessary to have a follow-up period after the study period. The subject will be instructed to contact investigator should he experience discomfort or other problems after the study. If investigator believes it is necessary to follow up on a subject it will be registered in the eCRF.

## 6.4.2. Activities performed by sponsor representatives

Sponsor (Clinical Manager or representative hereof) is responsible for:

- Training of investigator and study nurses in the study procedures, how to use the products, complete the eCRF and how to report possible safety issues to Sponsor. All training will be documented by site and sponsor by signing a Training Log
- Support during the recruitment process
- Monitoring

## 6.4.3. Foreseeable factors that may compromise the outcome/results

No foreseeable factors are expected to compromise the outcome/results of the investigation.

Flow chart

Error! Reference source not found.8 shows the scheduled visits and corresponding assessments for the study period

Activity	Visit 0	Visit 1	Visit 2
Oral and written information	(Inclusion) X		
Informed Consent Form	X		
Check of inclusion and exclusion criteria,			
including urine analysis	X		
Demographic and baseline data	X		
Allocation of subject number	^ X		
Randomisation			
Question subject about symptoms of UTI before Catheterisation	X	X	Х
Question subject about use of analgesics 24 hours prior to Catheterisation		X	Х
Urine sample for measuring endpoints (before catheterisation)		Χ	Х
Catheterisation per Randomisation		X	Х
Subject registration of overall discomfort during catheterisation (VAS)		X	Х
Subject registration of discomfort during nsertion and withdrawal of the catheter VAS)		Х	Х
Jrine sample for measuring endpoints after catheterisation)		X	X
Subject registration of discomfort during nicturition (VAS)		Х	X
Nurse registration of endpoints, including esults of urine analysis		Х	X
Concomitant medication		X	Х
Product accountability		X	X
Es/ADEs/SAEs/SADEs*		X	X
ermination form**			X

Table 8 Study period: Scheduled visits and corresponding assessments.

#### 6.4.4. Randomisation procedure

Each subject will be allocated randomly into one of two possible treatment sequences for the study period. Subjects are allocated to a randomisation number per a randomisation list generated automatically by computer (SAS, version 9.4).

At visit 0 investigator or his representative brakes a sealed, non-transparent envelope with the randomisation block inside. Randomisation number is registered in the electronic Case Report Form (eCRF) by investigator or his representative. The randomisation list is archived in Sponsor File.

\*Registered continuously. \*\*The Termination Form is filled out when the subject leaves the investigation, could be prior to visit 2.

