#### Inclusion Criteria:

## Justification for inclusion criteria:

- Have given written informed consent and signed letter of authority
- To ensure voluntarily and that the Helsinki declaration is met.

- 2. Be at least 18 years of age and have full legal capacity
- 3. Be a male
- 4. Willing to refrain from using analgesics¹ up to 24 hours prior to catheterisation visits
- 5. Have a negative urine multistix erythrocytes (microscopic haematuria)
- 6. Have a negative urine multistix:
- Leukocytes
- Nitrite

or if positive, subsequent negative for bacterial growth in urine culture (only conducted if positive leukocyte/nitrite multistix)

- 2. To meet the Helsinki declaration
- 3. Only males are included as their anatomy is considered 'worst case' due to a longer ure-thra.
- Pain relief could affect the primary and secondary endpoints of discomfort
- Haematuria is included in the study as it is a secondary endpoint. If a subject has haematuria at study start it could affect evaluation of data.
- 6. To ensure the subject does not have a urinary tract infection at inclusion

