#### 7. Statistical considerations

## 7.1. Statistical design, method and analytical procedures

Intention to Treat (ITT), Safety and Per Protocol (PP) populations will be defined at a formal data review meeting just before database lock. As a minimum, the clinical manager and the statistician will be involved in the classification of subjects.

The **ITT population** will be constituted by all randomized subjects with valid informed consent who have been exposed to at least one product, and with valid information on at least one product with respect to either primary or secondary endpoints. Any exclusion of subjects from the ITT set beyond this must be separately documented.

The **Safety population** (basis for AE summary) will be constituted by subjects that have given informed consent and have been exposed to at least one product.

The PP population will be constituted by a subset of ITT subjects

- who fulfil the inclusion/exclusion criteria
- where the primary endpoint may be evaluated for at least one of the two test days
- who do not violate the protocol in a serious way affecting the primary endpoint on all visits

Any exclusion of patients from the PP population must be documented.

Individual endpoints/data points may be excluded from analysis, even though the corresponding subject belongs to the ITT/PP population. This could for example be due to protocol violations at one test day that would affect the primary endpoint at the corresponding test day, but have no impact on the primary endpoint on the remaining test days. Any exclusion of endpoints/data points will be documented.

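### The sequence is opened at visit 0, although the check that decides whether a man is catheterised comes at visit 1, up to 7 days later

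*Combined protocol and SAP*

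**What the plan says.** Section 6.4.4 fixes the time of allocation: "At visit 0 investigator or his representative brakes a sealed, non-transparent envelope with the randomisation block inside". Section 6.4.1 agrees, under visit 0: "Enrolled subjects are allocated a subject number, and will hereafter be randomised per the study design". Table 2 also lists randomisation under visit 0.

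Visit 1 follows 0 to 7 days later, and section 6.4.1 allows the two visits on one day without requiring it. At visit 1 the man is asked about urinary symptoms and analgesic use, and his urine is tested for microscopic haematuria. If he is negative on all three, "the subject will be catheterised with product 1 per randomisation". The same procedure is repeated at visit 2.

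Three other provisions bear on this:

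- Section 7.1 limits the ITT set to "all randomized subjects with valid informed consent who have been exposed to at least one product", with valid data on at least one product. The PP set is a subset of it.
- Section 6.3.3 lets the investigator withdraw a man at any time in the man's best interest, and adds: "Withdrawn subjects will not be replaced by new subjects".
- Section 6.4.5 blinds only the subject, by a curtain. No section keeps the opened sequence from site staff.

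**The concern.** Allocation comes before the last decision on whether a man enters the comparison. A man can be randomised on one day, with his sequence known at the site, and be judged unfit for catheterisation several days later. If he is never catheterised, he is a post-randomisation exclusion and leaves both the ITT and PP sets. Non-inferiority must be shown in both.

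Two things are at stake. Exclusions made with the sequence known may not be neutral between sequences, and the ITT set then depends on decisions taken after allocation. Uneven losses also unbalance the two sequences, which widens the confidence interval for the same number of men. The plan gives no reason for opening the envelope this early.

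**Working it through.** **Order of events.** Sections 6.4.1 and 6.4.4 and Table 2 give: consent and criteria, envelope opened (visit 0); a gap of 0 to 7 days; symptom, analgesic and haematuria check (visit 1); first catheterisation. ITT membership starts only at the last step. Any loss between the second and last steps is therefore after randomisation and outside ITT.

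**Inputs for power.** Margin 1.2 cm, SD 1.6, within-subject correlation 0.5, true difference 0, 18 effective and 22 included men (section 7.2). Upper limit of the 95% confidence interval, taken as two-sided, so one-sided 2.5%; test day as a fixed effect (section 7.1). Equal allocation, 11/11, is assumed because section 6.4.4 gives no ratio.

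**The plan's own figure.** SD of the within-man difference = 1.6 × √(2 × (1 − 0.5)) = 1.6. A paired t-test with 18 men has SE = 1.6/√18 = 0.377, and the noncentral t distribution gives 85.0% power. With 17 men it gives 82.7%. The stated 18 is reproduced.

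**With test day in the model.** SE = 1.6 × √((1/n1 + 1/n2)/4), with n1 + n2 − 2 degrees of freedom:

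| Men left | Split by sequence | SE (cm) | Power |
|---|---|---|---|
| 22 | 11/11 | 0.341 | 91.7% |
| 21 | 11/10 | 0.350 | 90.2% |
| 20 | 10/10 | 0.358 | 88.7% |
| 20 | 11/9 | 0.360 | 88.4% |
| 19 | 10/9 | 0.368 | 86.8% |
| 19 | 11/8 | 0.372 | 86.0% |
| 18 | 9/9 | 0.377 | 84.8% |
| 18 | 11/7 | 0.387 | 82.9% |
| 17 | 9/8 | 0.389 | 82.2% |
| 17 | 11/6 | 0.406 | 78.9% |

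Losing 1 to 3 men leaves power between 90.2% and 86.0%, even if every loss is in one sequence. Imbalance alone costs 84.8 − 82.9 = 1.9 points when four are lost, and 82.2 − 78.9 = 3.3 points when five are lost.

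**Bias.** A simulation (40,000 runs per case) set the true difference at 1.2 cm, with an assumed period effect of 0.3 cm, and dropped the most sensitive men from the test-first sequence only.

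- Additive device effect, 0 to 4 men dropped: bias about 0, one-sided type I error 2.4% to 2.6%.
- Device effect assumed to grow by 50% per between-subject SD of sensitivity: bias −0.05, −0.08 and −0.17 cm, and type I error 3.2%, 4.1% and 5.8%, for 1, 2 and 4 men dropped.

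Nothing in the documents supports the sensitivity link. It shows what would be needed for material bias.

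**The case against.** The strongest reply is that a two-period crossover is robust to this. Every man is due both products, test day is modelled, haematuria is read by machine (section 6.4.5), and a man never catheterised has no VAS score under any ITT definition. The gap vanishes when visits 0 and 1 share a day. The 20% drop-out allowance absorbs the likely losses. All of this stands, and it makes the point small. It does not explain why the sequence should be known before the symptom and analgesic questions, or before a discretionary withdrawal.

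Several stronger readings are tempting but not supported:

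- **That early opening costs power for each man lost.** Section 7.2 already allows four losses. Sections 6.3.4 and 6.3.6 count the 22 at consent and section 6.3.3 bars replacement, so a lost man uses a place wherever the envelope is opened.
- **That men failing the visit 1 check are always lost.** Section 6.4.1 does not say whether they are rescheduled or withdrawn, and failing the check is not itself a listed mandatory withdrawal reason in section 6.3.3.
- **That a man may be randomised while his culture is pending.** Criterion 6 accepts a positive strip "or if positive, subsequent negative for bacterial growth in urine culture", but section 6.4.1 and Table 2 put fulfilment of the criteria before randomisation.
- **That baseline data are recorded after allocation.** The sentence in section 6.4.1 does not fix the order, and Table 8 lists baseline data above randomisation.
- **That the person who opens the envelope also makes the visit 1 check.** Section 6.4.1 does not say who asks the questions.
- **That one envelope reveals several men's sequences.** The word block in section 6.4.4 is ambiguous, and the next sentence registers a single randomisation number.

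**Conclusion.** The point holds as a free improvement, not as a threat to the trial's conclusion. Unless visits 0 and 1 coincide, site staff can know a man's sequence before the check that decides whether he is catheterised, and a man who does not go on is excluded after randomisation.

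Under the plan's SD and correlation, and assuming 11/11 allocation, 1 to 3 such losses keep power above the planned 85%. The measurable cost is imbalance: about 2 points of power at four one-sided losses and about 3 at five. Bias in the contrast is close to nil if the device effect is additive. It becomes noticeable only under an assumed link between device effect and sensitivity combined with selective exclusion, and the documents give evidence of neither. How many men would be lost between the envelope and the first catheterisation cannot be derived from the documents.

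**What to change.** - Open the envelope at visit 1, after the pre-catheterisation check is passed and immediately before the first catheterisation.
- State that each envelope holds one man's sequence only.
- Move randomisation to visit 1 in sections 6.4.1 and 6.4.4 and in Tables 2 and 8, and align the sentence in section 6.3 on when randomisation takes place.
- State how a man who does not pass the visit 1 check is handled. If the envelope stays at visit 0, report by sequence all men randomised but not catheterised.

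The cost is wording. No visit, staff or sample-size change is needed, and section 6.2 already supplies the site with 75 of each product. Losses before the first catheterisation then become pre-randomisation losses, and they can no longer be selected on a known sequence. The change does not restore numbers, since the 22 are counted at consent. Nor does it remove losses at the repeat check before visit 2, when the sequence is known under either scheme.

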#### 6.4.5. Blinding

The subject will be blinded with a curtain so he will not be able to see which catheter is used. The nurse is not blinded as it is not possible to blind the products due to visible differences.

It is a disadvantage that it is not possible to blind the nurses as there could be some bias in their assessment of the products tested. However, it is the subject who assesses the primary and secondary endpoints regarding discomfort (VAS) during catheterisation and micturition. Haematuria is measured automatically by computers, hence eliminating possible bias.

#### 6.4.6. Case Report Forms

Assessments and observations throughout the investigation for each subject and nurse will be carefully collected in the eCRF.

The eCRFs are supplied by the sponsor by a unique log on to the electronic Data Management System Rave EDC. Each eCRF is unique as it includes an identification number and is created for specifically for each subject. It is the responsibility of the investigator to ensure that all data are entered promptly and correctly.

The sponsor will be responsible for training the investigator and the study nurse in completion of the eCRF. The nurse will be responsible for guiding the subject on how to complete the subject's part of the CRF. The eCRF will clearly state which parts are to be completed by whom. The subject's part will be the pages regarding endpoints measured by the VAS-scale. These pages will be in Danish. After completion by subject, the study nurse or investigator will measure the VAS-scale and enter the measurement in the eCRF.

The investigator will keep a separate list of the subjects' ID numbers, names and addresses in a locked room/cabinet. Only data referred to in this clinical investigation plan will be recorded in the eCRFs.

## 6.5. Concomitant treatment

Subjects may not use analgesics 24 hours prior to catheterisation visits, see Inclusion and exclusion criteria section 6.3.1.

Subjects may not participate in other interventional clinical investigations during participation in this investigation.

#### 6.6. Monitoring plan

Planning of monitoring visits and monitoring is carried out by the Clinical Manager or delegate.

Before doing any review of subject data, the Clinical Manager or delegate must review the signed Informed Consent Form(s) and only monitor data from subjects with a correct signed Informed Consent Form.

The first monitoring visit at the site should be conducted as soon as reasonably possible after the first subject at the site has completed the first visit of the investigation to minimise systematic errors done by site.

Additional monitoring will be conducted in accordance to the recruitment rate:

Monitoring visit two (2) will be conducted as soon as possible after the completion of the first 11 subjects

Monitoring visit three (3) will be conducted as soon as possible after the completion of the last 11 subjects

Monitoring visit four (4), Close out visit, will be conducted as soon as possible after database lock

Written informed consent, in- and exclusion criteria and all adverse events occurring during the investigation will be 100% verified for timely completion for all subjects enrolled in the investigation. 100% source data verification between the subject recorded VAS-scale in the eCRF and the measurement of the scoring completed by the investigator/relevant staff will be performed.

Investigation Site File shall be monitored for 100% completion per the Investigation File Requirement Checklist (sponsor ref. number VV-0201336)

Monitoring activities conducted by the clinical manager or delegate will be documented in the site visit report applicable to the conducted visit. A summary describing the observation(s) and actions required shall be provided as soon as reasonably possible to the investigator after the conducted monitoring visit.

During the monitoring visits the Clinical Manager or delegate will monitor that labels at products, retail boxes and shipments boxes are intact and legible.

The Clinical Manager or delegate will have close contact to the site in the recruitment period to ensure that any concerns, problems or recruitment challenges are solved with the site in a timely manner.

